### State your secondary study objectives

**Aim 2:** Examine the impact of PainPac on pain severity, pain interference, pain self-efficacy, emotional distress, and quality of life (secondary outcomes for secondary aim).

**Hypothesis:** PainPac will demonstrate improvements in pain-related outcomes (e.g., self-efficacy, emotional distress) and quality of life for patients that are at least equivalent to the improvements experienced by PCST-Video participants.

**Aim 3:** Gather quantitative and qualitative post-treatment data on patients' preferences, confidence in using technology, barriers, and facilitators regarding PainPac to update and optimize PainPac for a future large randomized clinical effectiveness trial.

**Hypothesis:** This data will lead to optimization of PainPac to improve pain-related outcomes in cancer patients.

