**Statistical Design and Analyses.** A pilot trial (N=60) will be used to compare PainPac (n=30) to PCST-Video (n=30) on measures of feasibility (primary aim), burden, acceptability, engagement, and initial pain-related outcomes. Sample size was informed by pilot trial guidelines for RCTs of behavioral interventions,  and past similar studies, that suggest 30 participants per condition is sufficient for determining feasibility and acceptability, and feasibility of a future definitive trial. We anticipate no more than 25% attrition by 1 month post- baseline, based on previous psychosocial studies with cancer patients. Both groups of 30 participants are needed because we aim to demonstrate two types of feasibility: feasibility of the PainPac app, which only requires the 30 PainPac participants, and feasibility of the subsequent larger RCT (i.e., recruitment, assessments), which requires all 60 PainPac and PCST-Video participants. We are recruiting both sexes and all genders, and we expect a nearly equal sample size between sexes. To account for sex as biological variable, we will describe all outcomes disaggregated by sex. We will examine intervention effects and use this data to optimize PainPac. Aim 1. Feasibility (accrual, attrition, adherence), burden, acceptability, and engagement will be assessed post-treatment and descriptive statistics will be produced for PainPac and PCST-Video. Overall trial feasibility benchmarks include reaching target accrual (N=60) within 15 months and <25% attrition by 1 month post- baseline. Descriptive statistics will be used to report non-eligibility and refusal. Data of non-completers will be compared to completers. 75% completed will serve as our feasibility benchmark. If >25% of consented patients drop out, PainPac will not be considered feasible. We do not expect attrition to be greater in the PainPac condition compared to PCST-Video. PainPac feasibility benchmarks include protocol adherence indicated by calculating the degree to which participants are willing/able to complete study assessments (pre, post, follow- up) and the 4 PainPac skills modules or 4 PCST-Video sessions. 75% completed will serve as our benchmark. If >25% of consented patients do not complete the intervention (modules /sessions and assessments), PainPac will not be considered feasible. We expect adherence in the PainPac condition will be at least comparable to PCST-Video. Patient Burden will be measured as a continuous variable by assessing physical, emotional, and financial burden of engaging in the study intervention. We expect burden will not be greater in PainPac compared to PCST-Video. Patient Engagement will be assessed by electronic app data (e.g., PainPac weekly log-ins) and patient self-report defined as the

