
number of times per week they practice the coping skills.  $\geq 3$  times/week will serve as the benchmark; if participants log into PainPac and/or practice the coping skills  $< 3$  times/week, PainPac will not be considered engaging. We expect engagement in PainPac will be at least comparable to PCST-Video. Acceptability will be indicated by 80% of patients reporting satisfaction with PainPac and PCST-Video ( $M=3.2/4$ ) on the CSQ. Aim 2. Between-group differences at follow-up will be characterized using Cohen's  $d$  and 95% confidence intervals. Consistent with recommendations for small pilot RCTs of behavioral interventions, we propose a conservative approach that focuses on describing effect size estimates and their variability instead of testing for significant group differences. As this is a small trial intended to provide signals the intervention is promising and data for a larger trial, all pre- to post-intervention and 1 month variables will be characterized using graphs/plots and descriptive statistics (e.g., mean, standard deviations, range). We will examine the pattern of findings to determine the best analytic plan for the subsequent trial. Pain may vary based on pain medications and disease stage/treatment; we will describe these variables and include them, when appropriate, as covariates in future larger trials. The subsequent trial will be fully powered to test two active conditions. Given our proposed sample size ( $N=60$ ), an a priori power calculation using G-Power suggests we will have  $>80\%$  power to detect medium-sized effects of  $d=0.74$  ( $\alpha=0.05$ , two-tailed). However, as noted above, our analytic plan focuses on describing between-group differences rather than testing for significant effects. Aim 3. We will use methods from applied thematic analysis to analyze interview data. First, we will create a codebook a priori that corresponds to major content areas from the interview guide. The codebook will include a coding matrix with categories, codes, and definitions. The analysts ([name] and a study member) will segment interview transcripts into major content areas using Nvivo and then use an inductive and iterative approach to identify data-driven codes. As new codes emerge, they will be applied to previously coded sections until all relevant information is captured. All codes will be grouped into themes and subthemes. The analysts will meet to discuss coding and resolve discrepancies in interpretation, and maintain an audit trail of coding and analytic decisions. The study team will review the qualitative findings and develop action steps for modifying the protocol. All data will be used to optimize PainPac for a large randomized clinical effectiveness trial. We will optimize areas related to patient preferences, barriers, beliefs, and cultural tailoring to increase usability and engagement and meet user needs.

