All adverse events will be reported to Duke's IRB and the data safety officer in real-time. All data will be stored on a secure server with multiple backups created regularly. All interactions with study participants will be under the direction of a licensed clinical psychologist (PI: [name]). [name] is supported by a strong and experienced team of investigators, including [name], a senior investigator and licensed clinical psychologist. Study investigators and staff for this trial will be taught to monitor for any signs that participants are experiencing high levels of physical or emotional distress that need to be addressed outside the context of this trial. If this is determined to be the case, the PI will work directly with the participant to move forward in a way that is in the best interest of the patient. No participant will be kept in the trial if they are experiencing increased or extreme distress. [name] works directly with Cancer Patient Support and Care at Duke Cancer Institute as a practicing licensed clinical psychologist and as a supervisor to psychology trainees (i.e., advanced graduate students, clinical psychology doctoral interns); she is integrated into the psychosocial care program at the Cancer Center and has experience referring cancer patients who are distressed to appropriate psychosocial or psychiatric care within this large team of mental health professionals. She will use the same resources when making referrals for distress participants in this study.

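### Removal from the trial for distress makes later Aim 2 data missing for an outcome-related reason, and the plan does not say how such removals count in the 25% feasibility gates

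*Combined protocol and SAP*

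**What the plan says.** The rule is "No participant will be kept in the trial if they are experiencing increased or extreme distress". It appears in the same words in three places: the Emotional Upset paragraph of the risk section, Data & Safety Monitoring, and Protection Against Risk under Data Safety Management Reporting. None of them gives an instrument, a cut-off or a reference time for *increased*.

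Other text reads differently. Potential Risks (under Risk/Benefit Assessment) answers significant distress with consultation and, if needed, referral. In each of the three places, the sentences just before the rule concern high levels of distress needing attention outside the trial, with the PI working out a way forward with the participant.

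Aim 2 is to "Examine the impact of PainPac on pain severity, pain interference, pain self-efficacy, emotional distress, and quality of life". In the analysis section, "Between-group differences at follow-up will be characterized using Cohen's" *d* with 95% confidence intervals. No analysis set, missing-data method or assessment after removal is described. For people who do not finish, the plan says only "Data of non-completers will be compared to completers".

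Feasibility is the primary outcome and has two 25% gates. For attrition: "If >25% of consented patients drop out, PainPac will not be considered feasible", with the benchmark stated as "<25% attrition by 1 month post- baseline". For adherence: "If >25% of consented patients do not complete the intervention (modules /sessions and assessments), PainPac will not be considered feasible". Neither gate mentions participants whom the study team takes out.

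**The concern.** The rule acts on a variable that the trial also measures as an outcome. A participant removed before A2 contributes neither A2 nor A3 distress data; one removed because of A2 contributes no A3. Missingness then depends on distress itself, and summaries of whoever remains will tend to look better than the randomised group would have.

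The arms may also differ in how often distress is noticed. PCST-Video participants meet a therapist weekly for 45-60 minutes, and interventionists are trained to report concerns to the PI. PainPac has no therapist, and its described daily data cover pain and skills use. If more distressed participants were removed from PCST-Video, the Aim 2 contrast would tilt against PainPac.

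The primary outcome is also exposed. *Drop out* is not defined and no exemption is given, so on the natural reading a safety removal counts as a drop-out. With 30 participants in the app arm, one or two such decisions can matter to whether PainPac is called feasible.

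**Working it through.** **The plan's own figure.** For 30 per arm, d = 0.74 and two-sided alpha 0.05, a two-sample t-test has 80.5% power, which agrees with the stated figure of more than 80%. It is not in dispute, and Aim 2 is descriptive in any case.

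**Attrition gate.** Inputs:
- 30 PainPac participants (Data Analysis & Statistical Considerations).
- Failure above 25%. Since 7/30 = 23.3% and 8/30 = 26.7%, the gate fails at 8 or more.
- Background attrition p = 16%, the videoconference figure from the earlier trial in Background & Significance. Using it for the app is an assumption.
- Removal rate w. The documents give none, so 3.3% (about 1 of 30) and 6.7% (about 2 of 30) are assumed.

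Taking removals as independent of other drop-out, and all of them as counted within the window, the total loss rate is q = 1 - (1 - p)(1 - w), and P(fail) = P(X ≥ 8) for X ~ Binomial(30, q).

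| w | q at p = 16% | P(fail), p = 16% | P(fail), p = 20% |
|---|---|---|---|
| 0 | 0.160 | 9.5% | 23.9% |
| 3.3% | 1 - 0.84 × 0.967 = 0.188 | 18.9% | 36.6% |
| 6.7% | 1 - 0.84 × 0.933 = 0.216 | 31.4% | 50.3% |

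If the gate is read on all 60 participants (more than 25% means 16 or more), the p = 16% figures are 2.4%, 8.5% and 21.0%.

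**Which gate is hit.** A2 falls 4 weeks after A1, and the attrition benchmark closes 1 month after baseline. A removal between A2 and A3 therefore falls mainly on the adherence gate, which includes the follow-up assessment.

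**Aim 2, upper bound.** Assume normal scores and removal of exactly the worst fraction f of one arm. The arm mean falls by φ(z)/(1 - f) SD, where z is the 1 - f quantile.
- f = 5%: z = 1.645, 0.1031/0.95 = 0.11 SD.
- f = 10%: z = 1.282, 0.1755/0.90 = 0.19 SD (0.195 to three places).

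If the trigger for removal correlates only 0.5 with the outcome, these shifts halve.

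**Unequal removal, true d = 0.** On the same upper-bound basis, 10% removed from PCST-Video against 5% from PainPac gives a spurious d of about 0.10, against PainPac. Equal removal gives none.

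**Scale.** The 95% half-width for d near zero with 30 per arm is 1.96 × √(2/30) = 0.51.

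**The case against.** The strongest reply is that the consequences are modest and partly covered. Aim 2 is explicitly descriptive, and the possible bias is small beside the interval width. The team reports no significant distress caused by study procedures in earlier work, so removals may be few. The DSM report already lists reasons for attrition. Needing to remove distressed participants might itself be feasibility information. Assessments are also named as a possible source of upset, so continuing them after a removal is partly a participant-protection decision. All of this stands, and it limits both the size of the point and the form of the fix. It does not supply a counting rule or an assessment path after removal.

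Three stronger readings are tempting, and the documents do not support them.
- A reader might infer that the worst distress values are deleted. Nothing says recorded data are discarded: an assessment that prompts removal is already in the database, and only later ones are lost.
- A reader might take *increased* as any rise in score and conclude that removals alone would breach 25%. The surrounding sentences concern high levels of distress judged by the PI, and nothing ties removal to a change score. A rise first seen at A2 is also already recorded as the attrition window closes.
- A reader might treat unequal detection as established. It is an inference of unknown size. Both arms have the same assessment schedule, the coordinator reviews all assessments daily, staff check in about technology in both arms, and study staff as well as interventionists are trained to watch for distress.

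**Conclusion.** The point holds as a cheap improvement. Followed as written, the rule produces informative missingness in an Aim 2 outcome and, on the natural reading, feeds study-team removals into primary feasibility gates that do not provide for them.

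The feasibility effect is the more important one. About one or two removals among 30 would roughly double or triple the chance of failing the attrition gate, from 9.5% to 19% or 31%. This rests on 16% background attrition, the assumed removal rates, independence, and removals being counted as drop-outs within the window. The Aim 2 effect is at most 0.11 to 0.19 SD for 5% to 10% removed from one arm, which is small beside a half-width of 0.51. Any difference between arms in removal cannot be estimated from the documents.

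The conflict between mandatory removal and the consultation, referral or individual-course wording has to be resolved by the investigators. The clinical threshold is theirs to set.

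**What to change.** - Have the investigators reconcile Potential Risks, Emotional Upset, Data & Safety Monitoring and Data Safety Management Reporting on what happens when distress is identified.
- Separate stopping the intervention from leaving the study. Keep A2 and A3 open to participants who are willing and whom the investigators judge able to continue, and include those data in Aim 2.
- Count a participant as attrition only when assessments are actually missing.
- State how these participants count in the separate adherence gate. Someone who stops modules or sessions would fail it even with complete assessments.
- Report investigator removals for distress by arm. Hold the reason in the de-identified REDCap study database, because the plan bars medically sensitive data from the tracking database.

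The cost is protocol and consent wording, one data field, and a few extra follow-up contacts with people who have stopped the intervention. Decisions on stopping and referral stay with the investigators.

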#### **Data Safety Management Reporting**

Monitoring of data and safety procedures will ensure that the protocol is conducted in accordance with Good Clinical Practice (GCP), that data are of high quality and integrity, and that the facilities and staffing are adequate for continued participation in the study.

**Data Safety and Monitoring Plan.** This trial carries minimal risk. All patients in the trial will continue their usual care during the course of the trial, thus their doctors will provide monitoring of the patients' overall medical status. All research personnel who have direct contact with patients will be trained to observe and report any adverse event to the PI ([name]). The PI will report any adverse events to the institutional review board at Duke University and to the NIH. An adverse event is defined as any untoward medical occurrence during the clinical investigation that has a causal relationship to the study protocol. A serious adverse event is defined as any event which results in death, is immediately life threatening, results in persistent or significant disability/incapacity, patient hospitalization, or is serious for any other reason representing significant hazard. We will appoint one data safety officer who is a MD and not associated with this study. The appointed MD officer will have experience with clinical research and trials and have a thorough understanding of adverse events. The appointed data safety officer will also have an annual responsibility to evaluate our current system of assessment and intervention and identify any problems. All adverse events will be reported to Duke's IRB and the data safety officer in real-time. All data will be stored on a secure server with multiple backups created regularly.

**Protection Against Risk.** All interactions with study participants will be under the direction of a Licensed Clinical Psychologist ([name] [PI]). Interventionists in this trial will have experience with distressed

patients with chronic disease. They will be trained, specifically in the context of this trial, to monitor for any signs that participants are experiencing high levels of physical or emotional distress that need to be addressed outside the context of this trial. If this is determined to be the case, the PI will work directly with the participant to move forward in a way that is in the best interest of the patient. No participant will be kept in the trial if they are experiencing increased or extreme distress. Interventionists in this trial will be carefully trained to monitor participants' psychologist status and report to the PI. [name] (PI) will be contacted when emotional distress is identified in a participant. [name] works directly with the Cancer Patient Support Program at the Duke Cancer Institute as a practicing licensed clinical psychologist and as a supervisor to psychology trainees (i.e., advanced graduate students, clinical psychology interns); she is integrated into the psychosocial care program at the cancer center and has experience referring cancer patients who are distressed to appropriate psychosocial or psychiatric care within this large team of mental health professionals. She will use the same resources when making referrals for distress participants in this study.

There is the possibility of a breach of confidentiality. The consent form will address this possibility. All efforts will be made for confidentiality to be maintained by using case numbers to identify participants' research records and by having a limited number of individuals who have access to identifying information. Identifying information will be kept separate from research records. All research records will be kept in a locked file cabinet and password protected computer files. Only the PI and other trained research staff will have access to the research records. The PI has completed Duke University Health System Institutional Review Board's online training course: Protecting Research Subjects, which addresses confidentiality. All other individuals involved in this study will be required to complete this course and ongoing training.

**The Data and Safety Management (DSM) Report:** In addition to the above monitoring of data safety, there will also be a DSM Report generated quarterly by the CRC and data manager and presented to the PI. A full DSM report will be provided to the Data and Safety Monitoring officers annually or more frequently as needed. DSM Reports will contain the following:

- **Study Overview** with a review of study protocol, purpose of the study, primary outcomes, a description of key study personnel involved, and study timeline.
- **Recruitment Data** with total number of patients approached and screened, total participants enrolled, and data on reasons for inclusion/exclusion of potential participants.
- **Sociodemographic Data** from study participants with reference to expected age, racial, ethnic, sex, gender, and economic profiles.
- **Participant Retention** including a description of reasons for participant attrition.
- **Quality Assurance** including a report on data integrity processes, data transfer, encryption, any issues with paper and electronic data.
- **Regulatory Issues** including a report on IRB changes and protocol changes and the reasons for these changes.
- **Adverse Events** including a report on which events were study-related and which were not, how these AEs were managed and reported. Given that this is a behavioral virtual reality technology-based intervention focused on coping with pain, no medical emergencies are expected. However, if they arise, we will immediately contact the patient's oncologist. [name] (Co-I) directs the clinical psychology training program within the Duke Cancer Patient Support Program at the Duke Cancer Center. For psychosocial distress, the PI will contact [name] immediately to discuss the most appropriate course of action. If additional treatment is indicated, the PI and [name] will facilitate appropriate referrals. The PI and study team (Drs. [name] and [name] [Co-Is]) have conducted research in the proposed area and have not encountered significant psychological distress caused by study procedures.
- **Serious Adverse Events** including a detailed report on the individual(s) for whom this occurred, timing of the event, relationship to study procedures, timing and completion of reporting, and actions of Duke IRB, and the NIH as necessary. For the purpose of this behavioral trial, a SAE is defined as an event that, as a direct result of the study, causes serious harm to the subject (e.g., study involvement caused death or serious injury). We do not anticipate any SAEs.

#### Privacy, Data Storage & Confidentiality

- Complete the Privacy and Confidentiality section of the iRIS submission form.
